12.9 Non-Inferiority Margin

The NI margin to be used for the analyses summarized in Sections 12.5.2 and 12.6.1 will be 1.20.

12.10 Power for Analysis of Critical Secondary Variables

Sample size estimates were also performed using plausible assumptions for the occurrence of the first key secondary endpoint, a composite of the proportion of patients with hospitalisation or death related to major complications of device implantation (i.e., need for thoracotomy, pericardiocentesis, or vascular surgery) or complications of long-term device therapy (i.e., infection not leading to hospitalisation, lead and/or generator removal/replacement, inappropriate shocks, explantation).

The following assumptions were made for these sample size estimates:

- Superiority analysis
- Alpha = 2-sided 0.05
- Power = 80% and 90%
- 1:1 randomisation to AdreView™ and SoC groups
- Proportion of SoC patients with $H/M \geq 1.60$ who have composite endpoint of harm (summarized above) from ICD implantation = 5%, 6%, 7%, 8%, 9%, or 10%.
- Proportion of AdreView™ group patients with $H/M \geq 1.60$ who have composite endpoint of harm from ICD implantation = 0 (approximated by 0.0001).

Based on the above, the total sample size will range from 156 to 486 patients overall with a H/M ratio ≥ 1.6 .

Thus, the sample size estimated for the primary efficacy endpoint is also adequate for the first key secondary endpoint (assuming 24% of patients in both the AdreView™ and SoC groups will have a H/M ratio ≥ 1.6 , approximately 500 patients overall with a H/M ratio ≥ 1.6 is expected).

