12.8 Sample Size Calculation

Assumptions:

The all-cause mortality rate that is expected in the study has been estimated using the all-cause mortality rate observed in Study GE-122-016 at 36 months (internal report). It is assumed:

	Patients with $25\% \leq \text{LVEF} \leq 30\%$		Patients with $30\% \leq \text{LVEF} \leq 35\%$	
	%	Mortality Rate	%	Mortality Rate
H/M ratio <1.6	79%	20.25%	75%	15.14%
H/M ratio ≥ 1.6	21%	9.72%	25%	4.68%

In addition, the following observations or assumptions were taken: the ratio of patients with $25\% \leq \text{LVEF} \leq 30\%$ vs $30\% \leq \text{LVEF} \leq 35\%$ is expected to be 1:4 to account for the prior enrollment of only patients with $30\% \leq \text{LVEF} \leq 35\%$; the hazard ratio of patients with ICD implantation vs with usual care in the existing practice is 0.9 [Køber et al. 2016]. Referring to existing practice, only 15% of patients with $25\% \leq \text{LVEF} \leq 35\%$ currently receive ICD. Accordingly, the number of patients who currently do not receive ICD but who will receive it according to protocol and the number of patients who currently receive ICD and who will not receive it according to protocol have been calculated. In addition, the all-cause mortality rate of patients currently not receiving ICD but who will receive according to protocol (85% of patients with H/M ratio <1.6 in the AdreView™ group) has been corrected to take into account the 31% reduction in all-cause mortality observed at 20 months in the MADIT II trial [Moss et al. 2012]. These assumptions led to a composite mortality rate of 11.34% in the AdreView™ group and 13.33% in the SoC group. The sample size is estimated with the hypothesis of not having a relative increase of mortality rate in excess of 20% and with the following assumptions:

- Alpha = 0.025, 1-sided.
- Statistical power = 80%.
- 1:1 randomisation to AdreView™ and SoC groups.
- $H_0: \text{HR} \geq \text{HR}_0$ vs $H_1: \text{HR} < \text{HR}_0$. $\text{HR}_0 = 1.20$.
- Assumed HR: 0.84.
- Accrual time: 18 months.
- The total study duration: 48 months.
- AdreView™ group survival rate at 36 months: 0.887.

Based on the above assumptions, the required total number of events will be 247, and the required total number of randomized patients will be 2001.

The planned study accrual will be at least 2354 patients screened in order to randomize at least 2001 patients in the study.

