Sample size estimates were also performed using plausible assumptions for the occurrence of the first key secondary endpoint, a composite of the proportion of patients with hospitalization or death related to major complications of device implantation (i.e., need for thoracotomy, pericardiocentesis, or vascular surgery) or complications of long-term device therapy (i.e., infection not leading to hospitalization, lead and/or generator removal/replacement, inappropriate shocks, explantation).

The following assumptions were made for these sample size estimates:

- Superiority analysis
- Alpha = 2-sided 0.05
- Power = 80% and 90%
- 1:1 randomisation to AdreView™ and SoC groups
- Proportion of SoC patients with $H/M \geq 1.60$ who have composite endpoint of harm (summarized above) from ICD implantation = 5%, 6%, 7%, 8%, 9%, or 10%
- Proportion of AdreView™ group patients with $H/M \geq 1.60$ who have composite endpoint of harm from ICD implantation = 0 (approximated by 0.0001).

Based on the above, the total sample size would range from 156 to 486 patients overall with a H/M ratio ≥ 1.6 . Thus, the sample size estimated for the primary efficacy endpoint was also adequate for the first key secondary endpoint (assuming 24% of patients in both the AdreView™ and SoC groups will have a H/M ratio ≥ 1.6 , approximately 500 patients overall with a H/M ratio ≥ 1.6 was expected).

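### Protocol 12.10 overstates the low-risk count (480, not about 500), mixes methods in its size range, and calls the size adequate without stating the SoC ICD uptake on which adequacy depends

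*Protocol*

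**What the plan says.** Protocol 12.10 sizes the first key secondary endpoint, the composite of device-related harm in patients with H/M ≥1.6. Its settings are "Superiority analysis", "Alpha = 2-sided 0.05", "Power = 80% and 90" per cent, and 1:1 allocation. The SoC input is the proportion of SoC low-risk patients "who have composite endpoint of harm (summarized above) from ICD implantation = 5%, 6%, 7%, 8%, 9%, or 10" per cent; the AdreView proportion is zero, approximated by 0.0001. The section reports that "the total sample size will range from 156 to 486 patients overall" with H/M ≥1.6 are needed. It then takes 24% of patients as low risk, expects roughly 500 of them, and concludes: "Thus, the sample size estimated for the primary efficacy endpoint is also adequate for the first key secondary endpoint". SAP 2.3 repeats this in the past tense ("the total sample size would range from 156 to 486 patients overall").

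Four other places bear on ICD use in the SoC arm:

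- Protocol 12.8 (primary endpoint): "Referring to existing practice, only 15% of patients with" LVEF in the study range currently receive an ICD. It accordingly counts 85% of AdreView patients with H/M <1.6 as newly implanted.
- Protocol 6.1 and 9.3: SoC patients will undergo ICD implantation; 9.3 gives a 45-day target.
- Protocol Table 1, note h: SoC implantation follows each site's local standard of care.
- Protocol section 4: about half of guideline-eligible patients actually receive a device.

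Section 12.10 itself states no SoC uptake.

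**The concern.** Three things do not fit together.

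1. The expected count is wrong on the section's own inputs, and the correct figure falls on the other side of the largest stated requirement.
2. The two ends of the stated range do not come from one sample-size method.
3. A 5-10% rate of harm from implantation, spread over all SoC low-risk patients, needs many of them to carry a device. Section 12.8 describes the same arm with 15% carrying one.

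Under Protocol 12.6 this endpoint is tested first among the key secondaries, and a non-significant result stops the sequence. An adequacy statement that holds at one uptake and fails at another therefore matters for the whole key secondary family in the protocol's plan.

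**Working it through.** **Expected count.** 0.24 × 2001 = 480.2, so 480, or 240 per arm. The 1:4 LVEF mix in 12.8 gives 0.2 × 21% + 0.8 × 25% = 24.2%, and 0.242 × 2001 = 484. Both are below 486. A count of 500 corresponds to 25% of 2001.

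**Reproducing 156 to 486.** With p₁ the SoC rate, p₂ = 0.0001, d = p₁ − p₂ and p̄ = (p₁ + p₂)/2, the size per arm is

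m = [1.96·√(2p̄(1−p̄)) + z·√(p₁(1−p₁) + p₂(1−p₂))]² / d², where z is the normal quantile for the power,

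and the continuity-corrected size is m′ = (m/4)·[1 + √(1 + 4/(m·d))]².

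- 5%, 90% power: m = 204.03, d = 0.0499, m′ = 242.46, so 243 per arm and 486 in total. This matches the upper end.
- 10%, 80% power: m = 73.59, d = 0.0999, m′ = 92.5, so 93 per arm and 186 in total. This does not match 156; the uncorrected total is 148.
- 10%, 80% power, Fisher's exact test: 78 per arm has 80.2% power (77 has 79.2%), so 156 in total. This matches the lower end.

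| Method used throughout | 10%, 80% | 5%, 90% |
|---|---|---|
| Uncorrected | 148 | 410 |
| Continuity-corrected | 186 | 486 |
| Fisher exact | 156 | 370 |

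**480 against the requirements.** Of the 12 continuity-corrected scenarios (six rates, two powers), only 5% at 90% exceeds 480, by six patients; the next largest is 402. At 480, that scenario has 89.6% power by the corrected formula.

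**What 12.8 implies about SoC uptake.** Take the table's rates as mortality without an ICD (an assumption). The mix is 0.2 × (0.79 × 20.25% + 0.21 × 9.72%) + 0.8 × (0.75 × 15.14% + 0.25 × 4.68%) = 13.63%. Apply the 0.9 ratio to a fraction u, that is 13.63% × (1 − 0.1u):

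- u = 15%: 13.4%
- u = 50%: 12.9%
- u = 100%: 12.3%

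The stated SoC rate of 13.33% is not reproduced exactly, but of these three it lies nearest to 15% uptake.

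**What 12.10 implies.** At 15% uptake, 5-10% harm over all SoC low-risk patients would need 5/15 = 33% to 10/15 = 67% harm among those implanted. No section gives such a rate.

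**Power by uptake.** Assume 5-10% is harm per implanted patient. The SoC rate is then uptake × harm. Binomial outcomes were enumerated exactly with 240 per arm, 0.0001 in the AdreView arm, two-sided 0.05, without stratification. With no AdreView events, the uncorrected chi-square test rejects from 4 SoC events and Fisher's test from 6.

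| SoC uptake | SoC rate | Expected SoC events | Chi-square power | Fisher power |
|---|---|---|---|---|
| 15% | 0.75-1.5% | 1.8-3.6 | 10.5-47.6% | 1.0-15.1% |
| 50% | 2.5-5% | 6-12 | 84.1-99.7% | 54.9-98.0% |
| 100% | 5-10% | 12-24 | at least 99.7% | at least 98.0% |

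**Break-even.** By the normal approximation, 480 patients give 80% power once the SoC rate reaches 3.2% (4.0% with continuity correction). That is 65-80% uptake if harm per device is 5%, and 32-40% if it is 10%.

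**The case against.** The strongest reply is that 12.10 follows the design. Sections 6.1 and 9.3 say that SoC patients will undergo implantation, and inclusion criterion 4 requires that they be eligible for an ICD at their site. The 15% in 12.8 describes existing practice rather than trial conduct. If SoC patients are implanted as written, 480 is ample and the assumption that needs defending is in 12.8. This stands: the documents do not show that 12.10 is the section in error. Table 1 note h, which defers to local standard of care, leaves uptake open.

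The reply is also right on size. The 480 versus 500 slip is about 4%, 2001 is a stated minimum, and the planned Cochran-Mantel-Haenszel test is described without a continuity correction; uncorrected sizes peak at 410. Fisher's test is a legitimate source for 156, so the fault in the range is an unnamed and inconsistent method. It is harmless at the lower end, since 480 far exceeds both 156 and 186.

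Finally, SAP 5.4.4 drops hierarchical testing after early termination and reports all secondary endpoints for reference only, so nothing now stops at this endpoint. That limits the consequence to the protocol's plan. It does not remove the inconsistency between 12.8 and 12.10, or the adequacy claim that SAP 2.3 still carries.

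**Conclusion.** The adequacy statement is conditional on an uptake figure that the section does not give and that the documents treat inconsistently. Power runs from 1-48% at 15% uptake, depending on the test and the harm rate, to at least 98% at full uptake. This rests on reading 5-10% as harm per implanted patient, on 240 per arm, and on unstratified tests. The count should be 480, and the range mixes two methods; both are certain but small.

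A reader might infer three stronger conclusions that the documents do not support:

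- **That 480 makes the size inadequate.** It falls short in one scenario of twelve, by six patients (89.6% against 90% power).
- **That 12.10 assumes nearly every SoC patient has an ICD.** It states neither uptake nor harm per device, and 32-80% uptake would give 80% power depending on the latter. What can be said is that its rates imply use far above 15%.
- **That the endpoint is underpowered as designed.** That follows only if 12.8's 15% describes the SoC arm. If 6.1 and 9.3 do, the conflict lies in the primary mortality assumptions.

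**What to change.** In Protocol 12.10 and SAP 2.3:

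1. Replace the expected count with about 480 (240 per arm).
2. Recompute the range with one named method: 186 to 486 if continuity-corrected, 156 to 370 if Fisher exact, 148 to 410 if uncorrected.
3. State one assumed SoC ICD uptake, with its basis, and reconcile 12.8 and 12.10 to it. Do not carry the 15% into 12.10 by default; 6.1, 9.3 and Table 1 note h have to be reconciled with whichever figure is stated.
4. Tabulate power by uptake and harm per device.
5. Keep the adequacy sentence only if it holds at the stated uptake.

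The cost is text and one recalculated table, possibly with a less favourable stated power. If the reconciled uptake differs from 15%, the mortality inputs in 12.8 also need restating. Because SAP 5.4.4 has removed the hierarchy, for the SAP and the report the change corrects only the stated size and the adequacy claim; no analysis changes.

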12.11 Procedures for Missing, Unused and Spurious Data

Missing values will not be substituted by estimated values, but treated as missing in the statistical evaluation. All data from all patients in the study will be included in all listings, plots, summary tables, and statistical analyses when appropriate.

12.12 Rules for Excluding Patients from Analysis

All patients randomised will be included in the analyses unless otherwise specified.

12.13 Procedures for Reporting Deviations from Original Statistical Plan

Any deviations from the statistical analysis outlined in this protocol will be described, and reasons for the deviations listed, in the final Clinical Study Report.

13 SPECIAL REQUIREMENTS AND PROCEDURES

13.1 Regulatory, Institutional and Ethical Review

Before starting this study, the protocol (authorised by the Sponsor) will be submitted to the regulatory bodies/local health authorities (in accordance with local regulations) and to the IEC/IRB for evaluation. The protocol will also be signed by the principal investigator before submission to the IEC/IRB. The study will not start before the IEC/IRB gives written approval or a favourable opinion in accordance with ICH E6-GCP and all applicable regulatory bodies/local health authorities give approval or a favourable opinion as required.

No changes from the final approved (authorised) protocol will be initiated without the IEC's/IRB's prior written approval or favourable opinion of a written amendment, except when necessary to eliminate immediate hazards to the patients or when the change involves only logistics or administration. The Sponsor will authorise and the principal investigator(s) will sign the protocol amendment prior to submission to the IEC/IRB. Protocol amendments should be submitted to the IEC/IRB without delay.

13.2 Investigator's Responsibilities

13.2.1 Overall Responsibilities

The investigator(s) is/are responsible for conducting the study in full accordance with the Protocol and the Declaration of Helsinki, the *Good Clinical Practice: Consolidated Guideline*, approved by the ICH, and any applicable national and local laws and regulations. Information regarding any investigational centres participating in this study that cannot comply with these standards will be documented.

13.2.2 Patient Informed Consent

Written and oral information about the study in a language understandable by the patient will be given to all patients. Each patient's willingness to participate in the study will be documented in a signed and dated informed consent form before any procedures or assessments are done and after the aims, methods, anticipated benefits, potential hazards, and insurance arrangements in force are explained. It will also be explained to the patients that they are free to refuse entry into the study and free to withdraw from the study at any time without prejudice to future treatment. The informed consent process will be documented in the patient's medical record and the investigator will sign, date and time the informed consent form after the patient has signed, dated and recorded the time. The investigator(s) will keep the original consent forms and copies will be given to the patients.

13.2.3 Direct Access to Source Data/Documents

The monitor(s), auditor(s), authorised personnel of the Sponsor/CRO, health authority inspector(s) or their agents, and authorised members of IECs/IRBs will be given direct access to source data and documentation (e.g., medical charts/records, laboratory results, printouts, videotapes, etc.) for source data verification, provided that patient confidentiality is maintained in accordance with local requirements.

13.2.4 Confidentiality Regarding Study Patients

The investigator(s) must assure that the privacy of the patients, including their personal identity and all other personal medical information, will be maintained at all times. In eCRFs and other documents or image material (including materials from all examinations) submitted to the Sponsor/CRO, patients will not be identified by their names, but by an identification code (e.g., study patient number).

Personal medical information may be scrutinised for the purpose of verifying data recorded in the eCRF. This may be done by the monitor(s), properly authorised persons on behalf of the Sponsor, the quality assurance unit, or regulatory authorities. Personal medical information will always be treated as confidential.

13.3 Protocol Deviations

Any deviation from the protocol when no approved amendment exists must be documented as a protocol deviation and reported according to local requirements. If appropriate, corrective and preventative action must be implemented to avoid repetition. Protocol deviations and any potential impact on the study results will be discussed during the reporting of the study.

Waivers or protocol exceptions will not be granted prospectively by the Sponsor under any circumstances.

13.4 Study Monitoring

The Sponsor has ethical, legal and scientific obligations to carefully follow this study in a detailed and orderly manner in accordance with established research principles and applicable regulations. The investigator, as part of his responsibilities, is expected to cooperate with the Sponsor in ensuring that the study adheres to the protocol and GCP requirements.

Study monitoring will be performed in accordance with ICH E6-GCP, the Sponsor/CRO SOPs, the protocol, and applicable local regulations.

As part of a concerted effort to fulfil these obligations, the Sponsor will authorise a CRO to perform monitoring tasks and visit the centre(s) during the study as well as maintain frequent telephone and written communication. The investigator will permit the CRO personnel to monitor the study as frequently as is deemed necessary and provide access to medical records

to ensure that data are being recorded adequately, that data are verifiable and that the protocol is adhered to.

13.5 Audit and Inspection

According to ICH E6-GCP, the Sponsor or regulatory authorities may audit the investigational site. The Sponsor's Quality Assurance Unit, independent of the Clinical Research and Development Department, is responsible for auditing the study.

The investigator(s) must accept that regulatory authorities may conduct an inspection to verify compliance of the study with GCP.

13.6 Insurance

This study is covered under the Sponsor's Liability Insurance Policy (under General Electric Insurance Company and/or a company designated by the study Sponsor). A Certificate of Insurance and/or an information leaflet containing essential information about the insurance coverage can be provided upon request.

13.7 Publication Policy

Presentations, abstracts, posters, publications and any other scientific communications regarding the study protocol, conduct, and results will be managed by the ESC through a Publication Committee. The Publication Committee shall have the right to publish the results of their work conducted under this protocol, subject to providing the Sponsor with the opportunity to review the contents of any proposed abstract or publication concerning the work, including any results of the study, in advance of publication and if necessary to delay publication for a limited time not to exceed 60 days in order to protect the confidentiality or proprietary nature of any information contained therein. The Sponsor will make every reasonable effort to consider and release each proposed publication within 30 days, or proposed abstract within 15 days, of submission. Investigators shall comply with this policy.

15 APPENDICES

15.1 Information on Investigational and Registered Products

The reference document for this study is the IB. The reference document provides up-to-date information on the efficacy and safety of AdreView™, and is used for assessing expectedness of Serious Adverse Drug Reactions, in order to determine regulatory reportability. An unexpected adverse drug reaction is a reaction, for which the nature, seriousness, severity or outcome is not consistent with the applicable product information, e.g., the IB.

15.2 AdreView™ (Iobenguane I¹²³ Injection)

AdreView™ must be ordered for each specific use date. It is recommended that this order be placed a minimum of 2 weekdays (Monday through Friday) before the scheduled visit date. Orders placed less than 2 weekdays before the scheduled visit must be approved by the Sponsor.

If AdreView™ is to be administered in the morning, the patient should abstain from eating or drinking (other than water) after midnight on the day of AdreView™ imaging. If AdreView™ is to be administered in the afternoon, the patient may have a light breakfast, after which the patient should abstain from eating or drinking (other than water). The patient should lie quietly for at least 15 minutes prior to administration of AdreView™. The first set of images will be obtained at 3 hours and 50 minutes post-injection and will be comprised of an anterior planar imaging of the chest performed according to the Imaging Manual provided by the Sponsor. This image will be followed by SPECT acquisition in accordance with said manual. While the planar imaging will be used for the primary and secondary efficacy analysis, the SPECT imaging will be used for exploratory analysis

For each imaging procedure, the patient will receive AdreView™ at rest, administered as an intravenous injection. The activity of AdreView™ should be measured in a dose calibrator within 1 hour prior to the scheduled administration time. The activity and time of measurement will be recorded on the eCRF. Aseptic conditions must be observed during handling of a patient dose. AdreView™ does not contain preservatives. The Sponsor or the designated CRO may request to review the quality control log book on the calibrators.

AdreView™ must be administered on the date for which the product is calibrated and no later than 6 hours post-calibration time. The preparation should be stored at 20 to 25°C (68 to 77°F); excursions permitted to 15 to 30°C (59 to 86°F). Storage should take place in accordance with national regulations for radioactive material.

The administration of radiopharmaceuticals creates risks to other persons, from external radiation or contamination from spills of urine, vomiting, etc. Waste must be disposed of according to national regulations for radioactive material.

